1.0 BACKGROUND INFORMATION AND RATIONALE FOR STUDY

1.1 Introduction

Metastatic malignant melanoma remains a disease with a very poor prognosis and median survival duration of less than one year. Durable remissions with conventional therapy are rare and therefore clinical trials remain a primary treatment modality for metastatic disease. There are 2 currently FDA-approved therapies for metastatic melanoma. Chemotherapy with single agent parenteral dacarbazine or its oral pro-drug, temozolomide, are capable of producing responses in 6.5 to 20% of patients. These responses are usually minor to partial at best and are not durable (1). Combination with other chemotherapeutic drugs has not been successful (2). The immune system also seems to play a role in malignant melanoma. High dose Interferon therapy is the current standard therapy for the adjuvant treatment of stage IIB, IIC and III melanoma after surgical resection in which it has shown to result in modest improvements in DFS and OS (3). In metastatic disease, various immunologic approaches have been utilized as well. High dose IL-2 can produce a response rate of about 10-15% in patients with metastatic melanoma. About 5-10% of responses are complete and some of these complete responses are durable so that the lucky few patients who have a durable complete response are for all intents and purposes cured (4). Attempts to combine chemotherapy with immunotherapy, so called biochemotherapy, although improving response rates, has not impacted survival as summarized in recent meta-analysis (5).

A phase II trial of temozolomide followed by high dose IL-2 was conducted by UPMC (6). This study concluded that although it was safe to combine these agents and the combination had lower toxicity than previous biochemotherapy regimens, the overall response rates and durability of responses did not exceed those of single agent high dose IL-2. In this study, the patients received temozolomide at 75 mg/m² for 3 weeks continuously followed by high dose IL-2 off the temozolomide. This was repeated again and then response was determined. Responding and non-progressing patients received repeated courses up to 4 maximum. A course consisted of 2 cycles of high dose IL-2 as noted above with temozolomide for 21 days prior to each cycle. The overall response rate for the trial was 16.1%. CR rate was 9.7% and PR rate was 6.5%. Two of the 3 CR patients had durable responses. As noted, in this trial the temozolomide was given before the IL-2. We have reasons to suspect that the sequence of the two drugs as therapy would be crucial for response and indeed that is what led to the design of the current trial described below.

1.2 Rationale for Sequence-Specific Combination of High Dose IL-2 and Temozolomide in Metastatic Melanoma

As noted, we have recently observed that many patients who had received high dose IL-2 and failed to respond to it but who then go immediately to temozolomide seemed to enjoy extremely good responses which seem better quality and longer duration than typically observed for temozolomide alone. To date, we have observed 5 sequentially treated patients with metastatic melanoma who had failed high dose IL-2 but who then went on to receive immediate temozolomide given at 75 mg/m² per day for 21/28 days (7). Two of these patients had CRs, and 3 had very strong PRs. One CR has been durable to date which is a marked anomaly for single agent temozolomide. For comparison, in a recent phase II of extended low dose temozolomide alone given in the same manner as to the post-IL-2 patients noted above, the response rate was 12.5% and all of these were partial responses only. The median time to progression was 3.3 months (8). The responses that we observed were at a much higher rate of response as well as much better quality than expected for temozolomide alone as noted above. The responses were

also better than those observed when temozolomide was given first and then followed by high dose IL-2 in the UPMC study. We concluded that perhaps the major benefit we observed was a result of the prior high dose IL-2 therapy modulated by the temozolomide and that the sequence of treatment was clearly crucial for this response. We have not observed this effect in 2 patients who received dacarbazine post IL-2. These 2 patients had rapid progressive disease and died.

A possible explanation for this observation entails the T-reg population of lymphocytes (CD4+ CD25+) which act as natural brakes on the immune response and are the main contributors to immunologic tolerance and poor responses to immunotherapy against tumors. They comprise about 2-3% of CD4+ human T-cells. Patients with melanoma typically have high levels of T-reg cells and overactive T-reg cell function (9). These cells act to down-regulate any effective anti-melanoma immune response. Of interest, patients with melanoma who respond to high dose IL-2 have low levels of T-reg cells and their activity. It has been recently demonstrated in animals that low dose continuous temozolomide but not standard dose temozolomide can downregulate T-regs and their function (10). The low dose temozolomide that was given to our patients after they had completed and failed high dose IL-2 is completely compatible to the dosing that was used in this animal study. Based on our clinical experience of an unusually high rate of response in general and CR in particular in patients with melanoma receiving temozolomide post IL-2, we postulate that the temozolomide is acting to inhibit T-reg induction of tolerance resulting in better and somewhat more durable responses. The apparent sequence specific responsiveness noted is satisfactorily explained by this model. We hypothesize that incorporating low dose temozolomide after each cycle of high dose IL-2 for the up-front treatment of melanoma will improve response rate and allow more patients to go to additional course of IL-2 leading to increased CR rate, hopefully many of which will prove to be durable leading effectively to cure of the metastatic disease.

Both high dose IL-2 and temozolomide are FDA approved for use in metastatic malignant melanoma. They have been combined safely before as noted but without significant benefit when combined at least when the temozolomide is followed by the IL-2 (6). We feel that the combination needs to be sequence specific with the IL-2 given first to work. This is based on our ongoing clinical observations and the known effect of temozolomide on T-reg T-cells (7, 10). If a means to improve response, response durability and cure can be achieved with conventional available treatment merely through alterations in the sequence of delivery, this would prove to be a major and relatively cheap innovation in melanoma treatment. We therefore propose a prospective phase II trial to test this hypothesis directly together with appropriate correlative science immunoassays to see if the mechanism of response appears related to the depletion of the T-reg cells.

1.3 Study Synopsis

We propose a simple phase II trial of High Dose IL-2 followed by low dose temozolomide. The study would be a preliminary phase II efficacy trial and will be conducted using a modified Simon 2 stage design in up to 40 patients total. The historic overall response rate of high dose IL-2 in melanoma is about 5-10% with CR rate about 2.5 to 5%. The response to temozolomide alone is about 13% with CR rate of about 0%. We would hypothesize that the new combination therapy would increase response rate and CR rate by at least 2 fold compared to IL-2 alone based on our retrospective experience (7). Patients with metastatic melanoma who are considered good candidates i.e. ECOG <2, Creat<2.0 Bilirubin< 2.0 for a trial of high dose IL-2 would be offered participation. Patients with a history or clinical evidence of brain metastasis must have completed radiation therapy or surgical treatment of brain lesions and have no evidence of CNS

progression for at least eight weeks at the time of enrollment. Patients must not require corticosteroids for treatment of cerebral edema for brain metastases. Patients must be evaluated with a head MRI within 4 weeks prior to enrollment. Patients may have had prior dacarbazine or temozolomide since the mechanism of action of the temozolomide to be used in the context of this study is related more to effects on immune cells than to its known anti-melanoma effects. Patients would receive baseline staging imaging and laboratory assessment including study-specific immunologic correlative science testing. Patients would receive HD IL-2 according to standard procedure as in-patients on the PSHCI inpatient clinical unit. Patients would receive Cycle 1 of aldesleukin at 600,000 International Units/kg every 8 hours as tolerated up to a maximum of 14 doses. On or about day 10 after discharge from Cycle 1, they would be re-admitted for Cycle 2 of treatment. Then, 28 days after discharge from Cycle 2, they would receive temozolomide at 75 mg/m² daily for 21 days. Two cycles of HD IL-2 therapy as performed above plus 21 days of temozolomide would constitute one course of therapy. After this they would be scanned to assess response with CT/PET or CT(CAP). Responding patients (CR, PR, SD, Minor Response) would be given a 2nd course of treatment as above. Patients with a CR would receive one additional course of treatment and would then be observed. Patients with SD after 2nd course of treatment would go off study. Patients with a PR or Minor Response would continue treatment up to a maximum of 4 courses (8 cycles). If they develop Progressive Disease at any time during this treatment then they would go off study. If they develop a CR then they would have one additional course of treatment provided this course does not make more than 4 total courses. If they have PR or Minor Response after Course 2 then they would receive up to 2 additional courses.

2.0 STUDY OBJECTIVES

2.1 Primary Objectives:

- 1) To determine the clinical response (complete response, partial response, minor response, stable disease or disease progression) to high dose IL-2 followed by low dose temozolomide.
- 2) To determine the duration of response, and safety and toxicity of high dose IL-2 followed by low dose temozolomide.

2.2 Secondary Objectives:

- 1) To determine the quantitative effects of high dose IL-2 followed by low dose temozolomide on lymphocyte subsets, particularly the T-reg cells.
- 2) To determine the quantitative effects of high dose IL-2 followed by low dose temozolomide on cytokine production and anti-melanoma specific T-cell immune cells.
- 3) To determine the effects of high dose IL-2 followed by low dose temozolomide on autoimmune laboratory markers and clinical manifestations of autoimmunity.

3.0 STUDY DESIGN

This would be a non-randomized, open label, phase II, modified 2-stage preliminary efficacy study in patients with metastatic melanoma who are considered good candidates, i.e. ECOG <2, Creat <2.0, Bilirubin < 2.0 for a trial of high dose IL-2 treatment. Standard doses and delivery of both the high dose IL-2 and the temozolomide would be utilized. The total accrual goal for the trial would be up to 40 patients given in 2 stages. If no responses are noted in the first 12 patients accrued then the study will be terminated. If there is any response in the first 12 patients (CR, PR

or MR) then accrual of an additional 25 patients will ensue. Three additional patients would be allowed to accrue to cover any early drop-outs (receipt of less than 2 complete cycles of treatment). Eligible patients would have baseline imaging with CT or CT/PET. A head MRI to rule out asymptomatic occult brain metastases will be performed on all patients as well. Patients with known brain metastases will have baseline MRI done as well and would then have follow-up MRIs performed after each course. An echocardiogram to check cardiac function and PFTs with DLCO will be performed in all patients to assure that they have adequate cardiopulmonary reserve to sustain HD IL-2 as is standard. Patients would have baseline laboratory testing done pre-treatment and at every cycle initiation. An autoimmune panel will be performed pre-treatment and after every cycle of treatment. Correlative science immunoassays will be performed pre-treatment and after every cycle of treatment. Response as per radiologic imaging assessment and physical assessment of accessible and measurable skin metastases if applicable will be performed after every course of treatment (2 cycles HD IL-2 and 21 days of temozolomide.). Response will be determined after course 1 of treatment as a complete response (CR), partial response (PR), minor response (MR), stable disease (SD) or progressive disease (PD) according to standard definitions of response. Patients with CR will receive another complete course of treatment and will then go off study except for follow-up. Patients with progressive disease (PD) will go off study after course 1. Patients with stable disease (SD) after course one will repeat one additional course maximum. Patients with PR or MR will continue with additional courses as determined by response up to a maximum of 4 courses total (8 cycles). Responses and their durability will be compared to known rates of response and their durability using HD IL-2 alone. For a population of 40, using standard HD IL-2, the expected response rate 10% would be in 4 of the 40 and the CR rate 5% in about 2 of the 40. We would hypothesize that we can at least double these at a minimum using the methods described in this protocol.

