6.0 ASSESSMENTS

6.1 Clinical Assessments

The logistics of the study are summarized in the table, 15.1.8. Patients will be evaluated in the clinic by an investigator before each treatment cycle. Before each cycle of therapy, patients will have routine and correlative science labs performed along with a history and physical examination. These data will be recorded on a form (15.1.4 Clinical Evaluation). An adverse event form will also be completed at each of these evaluations by the study nurse-coordinator (see below). Patients will have staging performed with CT/PET or CT (CAP) after every complete course of treatment (2 complete cycles of HD IL-2 plus 4 weeks of rest plus 3 weeks of oral temozolomide plus 2 weeks of rest prior to reimaging = 1 complete course = approximately 12 weeks). Patients with measurable skin and/or subcutaneous lesions would have 2-dimensional measurements performed using a ruler after each complete course of therapy. They will also have an autoimmune panel drawn after each complete cycle. The autoimmune panel will include an ESR, CRP, ANA, RF, and TSH. Patients with known brain metastases will have repeat MRI of the head after each course. Patients with or without known brain metastases can get repeat MRI at any time should they develop neurologic symptoms as determined by the investigator. Response will be by modified RECIST criteria 1.1 and will employ the following definitions of response:

CR – complete response - no evidence of disease, 100% reduction in the volume of disease

PR – partial response - $\geq 50\%$ but $< 100\%$ reduction in volume of disease

MR – minor response - $\geq 25\%$ but $< 50\%$ reduction in volume of disease

SD – stable disease - $< 25\%$ increase in volume of disease to $< 25\%$ reduction in volume of disease

PD – progressive disease - $\geq 25\%$ increase in volume of disease

The final response will be the best response observed during the course of treatment while on study

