8.0 DATA ANALYSIS AND STATISTICAL METHOD

8.1 Sample Size Determination

The study will employ a Simon 2-stage optimal design with the following specifications: $p_0 = 0.05$, $p_1 = 0.20$, $\alpha = 0.10$, $\beta = 0.10$, where p_0 is the ineffective response rate, p_1 is the effective response rate, α is the false positive rate, and β is the false negative rate. With these specifications, a 2-stage Simon optimal design, which minimizes the expected sample size given an ineffective response rate, will enroll a total of 37 patients with 12 during stage 1 and 25 during stage 2. If there is no response among the first 12 patients, then the drug is considered ineffective and the enrollment will be stopped. Otherwise, the study will proceed to stage 2. The drug will be considered effective if there are at least 4 responses by the completion of the trial.

The design will assure good statistical power with respect to differentiating response rates of 5% and 20% (12). Three additional patients will be enrolled to allow for dropouts to a total of 40.

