8.2 Efficacy Determination

Efficacy analysis will be performed on the intention-to-treat set, which comprises of all patients enrolled in the trial. Patients must have completed at least one complete course (2 cycles) to be considered for response assessment. Patients receiving less than one course will be considered drop-outs from the study in terms of response. Patients who do complete at least one course of treatment will be classified as responders or non-responders. The overall response rate, which is the proportion of the responses among patients in the intention-to-treat set who have completed at least one complete course, will be obtained. In addition, a 95% confidence interval for the overall response rate will be constructed. Responses will be recorded after each course of therapy and will be tabulated as complete response, partial response, minor response, stable disease or progressive disease. Only PR and CR will be included in the numerator of the analysis for overall response but all responses will be recorded. The time to progression (TTP) in months for each patient will be recorded to ascertain the durability of the responses. Waterfall plots for a continuous assessment of response will also be generated. Correlative science results will be studied by non-parametric methods for differences in a given individual over time and between individuals.

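### Section 3.0 lets a minor response open stage 2, but only CR and PR count as response in section 8.2, so the Simon optimal design claimed in section 8.1 is not the design as written

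*Combined protocol and SAP*

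**What the plan says.** - **Section 3.0, stage-1 rule.** Stage 2 opens on any of three categories: "If there is any response in the first 12 patients (CR, PR" "or MR) then accrual of an additional 25 patients will ensue".
- **Section 6.1.** MR is a category of its own, a reduction of at least 25% but under 50%, and lies below PR.
- **Section 8.1, stage-1 rule.** "If there is no response among the first 12 patients, then the drug is considered ineffective and the enrollment will be stopped".
- **Section 8.1, final rule.** "The drug will be considered effective if there are at least 4 responses by the completion of the trial". Neither rule in 8.1 says which categories count as a response.
- **Section 8.1, claimed property.** The design is described as "a 2-stage Simon optimal design, which minimizes the expected sample size given an ineffective response rate".
- **Section 8.2.** "Only PR and CR will be included in the numerator of the analysis for overall response but all responses will be recorded".
- **Section 1.3.** The trial "will be conducted using a modified Simon 2 stage design in up to 40 patients total". Section 3.0 also calls the design modified. Neither section says what was modified, and 8.1 presents the standard optimal design.

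**The concern.** A Simon design has its published error rates, early-stopping probability and expected size only if the same binary response is counted at both stages. Here the interim gate accepts a lesser outcome than the final analysis. A more lenient gate is permissible, but it is a different rule and its properties must be calculated for that rule.

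Two things are at stake. First, the zero-in-12 rule is the only provision in the documents for stopping the trial for lack of efficacy, and admitting MR weakens it. Second, the go/no-go decision is ambiguous. With no CR or PR and a single MR among 12, one section leads to 25 more patients and another leads to closure.

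**Working it through.** **Inputs.** From section 8.1: p0 = 0.05, p1 = 0.20, alpha = beta = 0.10, 12 patients in stage 1, 25 in stage 2, 37 in total, stop on 0 of 12, effective on at least 4. From 8.2: the final count is CR+PR. Assumed, because the documents give no figure: an MR rate q of 2.5%, 5% or 10%, meaning patients whose response is MR and not CR or PR. The CR+PR rate is p.

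**Formulas.** Under the 3.0 gate the trial stops only if none of 12 patients has CR, PR or MR:

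- P(stop) = (1 − p − q)^12
- Expected N = 12 + 25 × (1 − P(stop))
- P(declared effective) = P(Bin(37, p) ≥ 4) − P(stop) × P(Bin(25, p) ≥ 4)

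The last line holds because a stopped trial has no CR or PR in stage 1, so any would-be total of 4 or more would have to come from the other 25 patients. Setting q = 0 gives the 8.1 design with CR+PR at both stages.

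The binomial terms are:
- At p = 0.05: P(Bin(37) ≥ 4) = 0.1119 and P(Bin(25) ≥ 4) = 0.0341.
- At p = 0.20: 0.9550 and 0.7660.

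**Step 1: the plan's own design (q = 0).**
- At p = 0.05: P(stop) = 0.95^12 = 0.540; expected N = 12 + 25 × 0.460 = 23.5; alpha = 0.1119 − 0.540 × 0.0341 = 0.0935.
- At p = 0.20: P(stop) = 0.80^12 = 0.069; power = 0.9550 − 0.0687 × 0.7660 = 0.902.

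A search over two-stage designs with these limits returns the same one (0 of 12, 3 of 37) as optimal. The 8.1 arithmetic is right for a single definition of response.

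**Step 2: the rule written in 3.0, with CR+PR at the end.**

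| Assumed MR rate | P(stop), p = 0.05 | Expected N, p = 0.05 | Alpha | P(stop), p = 0.20 | Power, p = 0.20 |
|---|---|---|---|---|---|
| 0 (8.1 design) | 0.540 | 23.5 | 0.0935 | 0.069 | 0.902 |
| 2.5% | 0.392 | 27.2 | 0.0985 | 0.047 | 0.919 |
| 5% | 0.282 | 29.9 | 0.102 | 0.032 | 0.931 |
| 10% | 0.142 | 33.4 | 0.107 | 0.014 | 0.944 |

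Alpha reaches 0.10 when P(stop) = (0.1119 − 0.10)/0.0341 = 0.349, which is q = 0.95 − 0.349^(1/12) = 0.034. It cannot exceed 0.112, the value with no interim stop.

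**Step 3: how often the two definitions disagree.** The chance of no CR or PR but at least one MR in 12 is 0.95^12 − (0.95 − q)^12 at p = 0.05. This is 0.148, 0.258 and 0.398 for the three MR rates.

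**Step 4: when staging stops saving patients.** A single-stage trial of 32 patients needing at least 4 responses meets the same limits (alpha 0.074, power 0.907). Expected N under the 3.0 gate reaches 32 when P(stop) = 1 − 20/25 = 0.20, which is q = 0.95 − 0.20^(1/12) = 0.0755. Above an MR rate of about 7.6%, the two-stage trial is on average larger than that single-stage trial when the treatment is ineffective.

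**Step 5: if MR were also counted in the final 4.** Section 8.2 does not imply this reading, but 8.1 does not exclude it. Running the 8.1 rule at total rates of 0.075, 0.10 and 0.15 gives probabilities of declaring the treatment effective of 0.26, 0.45 and 0.75 at a true CR+PR rate of 5%.

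**The case against.** The strongest reply is that the sections can be read together. Section 3.0 is the only place that names the categories opening stage 2. Section 8.2 governs only the overall response numerator. Calling the design modified would then signal a deliberately lenient gate followed by a strict final test. That reading is coherent, but it leaves 8.1 claiming an unmodified optimal design and a minimum expected size that the 3.0 rule lacks at any MR rate above zero. No properties are given for the modified rule.

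A second point stands as a caveat. Section 6.1 takes the best response on study as final, and patients with MR may go on to further courses, so an MR at first restaging may later become a PR or CR. The calculation treats MR as a patient's final category. If the gate is read at first restaging, some interim MRs belong to the CR+PR group, and for them the lenient gate avoids a wrong stop. The disagreement figures of 15%, 26% and 40% would then not all concern non-responders. The documents do not say when the 12 patients are assessed for the gate.

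It is also true that the error-rate effect is small, that power rises, and that the size of the futility loss depends on an MR rate the documents do not supply. Its direction needs no assumed value, only an MR rate above zero, and the conflict between sections needs no rate at all.

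**Conclusion.** The concern holds and should be fixed. The stage-1 rule in 3.0 is not the rule whose properties 8.1 claims. The main consequence is weaker stopping for futility: at a CR+PR rate of 5%, the chance of stopping after 12 patients falls from 54% to between 39% and 14% for assumed MR rates of 2.5% to 10%. This is not a case of serious alpha inflation under the reading 8.2 implies, nor of a wrong sample size. The figures assume 37 evaluable patients, a final count of CR+PR, and MR as a final category.

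**What to change.** **Preferred.** In 3.0, limit the stage-1 trigger to CR or PR. In 8.1, write CR or PR in both the stage-1 and final rules. Tabulate MR descriptively, as 8.2 already provides. The 8.1 design then stands as calculated.

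**Alternative.** If the sponsor wants the lenient gate, keep it and say that it is the modification. Drop the optimal claim, define the final rule as CR or PR, and report alpha, power, early-stopping probability and expected size over a range of MR rates. This option also suits a sponsor who expects interim MRs to deepen.

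Under either option, state when the 12 patients are assessed for the gate.

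**Cost.** A wording amendment to 3.0 and 8.1, with sample size and cut-offs unchanged. Compared with the lenient gate, the preferred option makes a stage-1 stop at a true 20% rate more likely (6.9%, against 4.7%, 3.2% or 1.4%) and gives power of 0.902 instead of 0.919 to 0.944. The 90% power planned in 8.1 already allows for this.

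### A single-arm trial compared only with IL-2 alone cannot test the sequence hypothesis, and its success bar lies below the plan's own temozolomide-alone and reverse-order response rates

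*Combined protocol and SAP*

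**What the plan says.** Section 1.2 holds that the combination works only if IL-2 comes first, and continues: "We therefore propose a prospective phase II trial to test this hypothesis directly", alongside immunoassays of T-reg depletion.

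The planned comparison is in Section 3.0: "Responses and their durability will be compared to known rates of response and their durability using HD IL-2 alone". The reference figures there are for 40 patients on IL-2: "the expected response rate 10% would be in 4 of the 40 and the CR rate 5% in about 2 of the 40". The target follows: "We would hypothesize that we can at least double these at a minimum using the methods described in this protocol". The synopsis (1.3) uses the same comparator, expecting the combination to "increase response rate and CR rate by at least 2 fold compared to IL-2 alone".

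The protocol also quotes two closer results, as background only:
- Temozolomide alone, in 1.3: "The response to temozolomide alone is about 13% with CR rate of about 0" percent. Section 1.2 gives 12.5%, all partial responses, for an extended low-dose schedule.
- Temozolomide followed by IL-2, in 1.1: "The overall response rate for the trial was 16.1%. CR rate was 9.7% and PR rate was 6.5" percent.

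Section 8.1 tests a fixed 5% against 20% and names no comparator. It stops at 0 of 12 and calls the drug effective at 4 or more responses in 37. Section 8.2 plans a CR+PR rate with a 95% confidence interval and no benchmark.

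**The concern.** Two things change between IL-2 alone and this regimen: an active drug is added, and it is added in a particular order. A comparison with IL-2 alone shows at most their combined effect. A regimen with no sequence or T-reg effect, performing like temozolomide alone or like the reverse order, could still meet the success rule. If that result were read in the light of Section 1.2, it would be taken as support for the sequence.

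This is separate from whether 5% is the right null rate. Raising the null to the IL-2 rate would still leave out temozolomide's own activity and the reverse-order result.

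**Working it through.** **Inputs.** From 8.1: p0 = 0.05, p1 = 0.20, alpha = beta = 0.10, stages of 12 and 25, stop at 0/12, effective at 4 or more of 37. From 3.0: IL-2 alone at 10% response and 5% CR, so doubling in 40 patients means 8 responses and 4 CRs. From 1.3: IL-2 alone at 5% to 10%, temozolomide alone at 13% with CR about 0%. From 1.1: reverse order at 16.1% response and 9.7% CR.

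**Step 1: reproduce the plan.** The probability of declaring the drug effective at true rate p is

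P(p) = sum over k = 1 to 12 of Bin(k; 12, p) × P[Bin(25, p) ≥ 4 − k].

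This gives P(0.05) = 0.0935 and P(0.20) = 0.902, both within specification. A search for the smallest expected sample size at 5% returns the same design (expected N 23.5). The Simon calculation is correct.

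**Step 2: apply the rule at the plan's other rates.** The bar is 4/37 = 10.8%.

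| True CR+PR rate | Source | P(declared effective) |
|---|---|---|
| 5% | p0 | 0.093 |
| 10% | IL-2 alone, 3.0 | 0.447 |
| 12.5% | temozolomide alone, 1.2 | 0.619 |
| 13% | temozolomide alone, 1.3 | 0.649 |
| 16.1% | reverse order, 1.1 | 0.796 |

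These figures assume 37 evaluable patients and one definition of response at both stages. Section 3.0 also lets a minor response open stage 2, which could only raise them.

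**Step 3: the doubling target.** Section 3.0 asks for both response and CR to double, so the relevant event in 40 patients is at least 8 responses including at least 4 CRs. Treat CR, PR and non-response as multinomial:

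sum over c ≥ 4 of Bin(c; 40, pCR) × P[Bin(40 − c, (pR − pCR)/(1 − pCR)) ≥ 8 − c].

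- Reverse-order rates (pR = 0.161, pCR = 0.097): 0.28.
- Additive model. This assumes independent action with no sequence effect: pR = 1 − (1 − 0.10)(1 − 0.13) = 0.217, with pCR = 0.05 because temozolomide contributes about 0% CR. Result: 0.13.

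Taken singly, the components look much easier. Eight or more responses occur with probability 0.31 at 16.1% and 0.66 at 21.7%. Four or more CRs occur with probability 0.55 at 9.7%, but only 0.14 at 5%.

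**Step 4: precision of the reverse-order benchmark.** Section 1.1 mentions 3 CR patients. 3/0.097 ≈ 31, so 16.1% is about 5/31 (an inference). The exact 95% interval is 5.5% to 33.7%.

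**Step 5: comparability.** In the reverse-order trial (1.1), 21 days of temozolomide preceded each of the two IL-2 cycles in a course. Here there is one 21-day block per course of about 12 weeks (5.3, 6.1). The temozolomide-alone figure in 1.2 comes from a schedule described as the one the post-IL-2 patients received, 21 of every 28 days. Exposure therefore differs from both benchmarks, as well as order.

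**The case against.** The best defence is that IL-2 alone is the right comparator for much of what the plan says. Section 1.2 also hypothesises that adding temozolomide after IL-2 will raise response and CR rates, and 1.3 frames the gain against IL-2. The primary objectives in 2.1 do not mention sequence, and 8.1 says only that the drug will be considered effective. This stands. A reader might infer that the plan will report 4/37 or a doubling as proof of sequence, but no section says so. The fault is confined to the direct test promised in 1.2.

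A reader might also infer from the single-component figures in Step 3 that doubling would come easily without any sequence effect. The documents do not support that, because the target covers response and CR together. The additive model is itself generous: it credits temozolomide with its full 13% at lower exposure.

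The sponsor could add that 1.1 describes the reverse order as no better than IL-2, so beating IL-2 is enough. That fails on the plan's own figures. Section 3.0 puts IL-2 at 10% and the reverse order gave 16.1%, so a result between the two beats one and not the other.

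The T-reg assays bear on mechanism. Without a reverse-order or temozolomide-only group they do not test sequence either.

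Finally, it is tempting to set a higher bar for a sequence claim, such as 10 of 37, the smallest count with a one-sided tail at or below 0.10 against 16.1% (0.063). That treats an imprecise benchmark as known. Set against 5/31, 10/37 gives a two-sided Fisher p of 0.38, and exposure differs as well as order. No count in this single arm can support the claim.

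**Conclusion.** The point holds as a limit on what the trial can conclude. The design does not test the sequence hypothesis directly, and its formal success bar of 10.8% sits below both closer benchmarks in the protocol. It passes 65% of the time at 13% and 80% at 16.1%. The joint doubling target is less permissive, at about 28% under reverse-order rates and about 13% under the additive model, but it too is set only against IL-2 alone.

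The 65% and 80% describe the 5% null rule applied to the quoted rates as if they were true. The 13% rests on the independence assumption and on 10% response and 5% CR for IL-2. The sample size calculation is not at fault.

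**What to change.** Keep the Simon rule and the sample size, and set no response threshold for a sequence claim.

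- **8.1 and 8.2:** state that 4 or more of 37 shows only activity of the regimen above 5%.
- **1.2 and 3.0:** replace the claim of a direct test of sequence with a statement that the result cannot establish a sequence benefit, which would need a concurrent comparison.
- **3.0 and 8.2:** report the CR+PR and CR rates, with the planned 95% confidence interval, descriptively against IL-2 alone, temozolomide alone and the reverse-order combination. Note that temozolomide exposure differs across these studies and that 16.1% is imprecise (about 5% to 34% if it is 5/31).

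The changes are to wording and reporting only, with no added patients, visits or procedures. The price is a narrower and less favourable claim.
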